12. TRIAL MANAGEMENT AND GOVERNANCE

The ELSA Trial Office is in the General Services Building at University of Alabama at Birmingham, and provides day to day support for the trial.

The primary investigators take responsibility for the design, execution, data collection, and data analysis for the study. The primary investigators also take responsibility for monitoring the study for safety and unanticipated adverse events/effects. The study team will meet at least once monthly during the study period.

The principal investigators will ensure that adequate systems are in place for monitoring the quality of the trial and appropriate expedited and routine reports, to a level appropriate to the risk assessment of the trial.

The manufacturers of the coils and vascular plugs have no role in the design, conduct, analysis, or reporting of the trial.

Data collected during the course of the research will be kept strictly confidential and accessed only by members of the trial team. Participant's details are stored on a secure database and regular checks and monitoring are in place to ensure compliance. The data manager (in collaboration with the Principal Investigators) manages access rights to the data set. Participants are allocated an individual specific trial number and their details are anonymized on the secure database.

13. HUMAN SUBJECTS RESEARCH

13.1 FDA Requirements

This study will enroll 50 patients with splenic injuries. The study interventions are approved by the Food and Drug Administration (FDA) as a Class 2 under 21 CFR 892.1600. Because it is a nonsignificant risk device being used in accordance with its defined indications, an FDA Investigational Device Exemption (IDE) is not required.

13.2 Potential risks

The potential risks of splenic artery embolization include unintentional blockage of other arteries, unintended movement of the coils or plugs, vascular injury, ineffective treatment/continued bleeding in the spleen, injury at the vascular access site, infection, kidney injury from the x-ray dye, and infection.

Study participants experience the risk of randomization such that the procedure group to which they are allotted may or may not be as effective and/or safe as the other arm.

14. ADVERSE EVENT/EFFECT REPORTING

14.1 Definitions and classification

All untoward medical occurrences will be classified by:

- a) Whether they involved a trial participant
- b) Were related to the use of the devices
- c) Seriousness
- d) Whether anticipated/unanticipated.

Note that adverse events are non-device-related medical occurrences, whereas adverse effects are caused by the investigational device or procedure.

14.1.1 Untoward medical occurrence

An untoward medical occurrence is an unintended disease or injury or untoward clinical sign in a trial participant caused by or related to the investigational device, device-related procedure, or comparator. Not all complaints about investigational devices have to do with untoward medical occurrences. If a complaint does not involve a trial participant or other person, it is not medical and is called a "non-medical complaint." Non-medical complaints do not need to be logged.

14.1.2 Adverse events

If the untoward medical occurrence did involve a trial participant, but was not related to the device, it is an adverse event. These events are further classified as serious adverse events or non-serious adverse events (AE).

14.1.3 Serious adverse events

Serious adverse events are untoward medical occurrences in a subject that are not related to the investigational device, comparator, or trial procedures, but that meet the criteria of "serious." A serious adverse event is one that:

- a) Led to a death
- b) Led to a serious deterioration in the health of the subject that:
 - i. Resulted in a life-threatening illness or injury, or
 - ii. Resulted in a permanent impairment of a body structure or a body function, or
 - iii. Required in-patient hospitalization or prolongation of existing hospitalization, or
 - iv. Resulted in medical or surgical intervention to prevent life threatening illness or injury or permanent impairment to a body structure or a body function
 - v. Led to fetal distress, fetal death, or a congenital abnormality or birth defect.

A planned hospitalization for a pre-existing condition or a condition required by the protocol, without serious deterioration in health, is not considered serious.

14.1.4 Adverse device effects

An untoward medical occurrence that happened in a subject and is related to the device or device procedure is an adverse device effect. If the occurrence does not meet the definition of serious, it is classified as an adverse device effect (ADE). Adverse device effects are a subset of adverse events.

14.1.5 Serious adverse device effects

An untoward medical occurrence that happens in a subject, is related to the investigational device, or procedure, and is serious, but is not unanticipated is a serious adverse device effect (SADE). Untoward medical occurrences that are not unanticipated, i.e. are unsurprising, are identified in the investigator's brochure or protocol and informed consent form.

As with serious adverse events, a serious adverse device effect is one which

- a) Led to a death
- b) Led to a serious deterioration in the health of the subject that:
 - i. Resulted in a life-threatening illness or injury, or
 - ii. Resulted in a permanent impairment of a body structure or a body function, or
 - iii. Required in-patient hospitalization or prolongation of existing hospitalization, or
 - iv. Resulted in medical or surgical intervention to prevent life threatening illness or injury or permanent impairment to a body structure or a body function
 - v. Led to fetal distress, fetal death, or a congenital abnormality or birth defect.

A planned hospitalization for a pre-existing condition or a condition required by the protocol, without serious deterioration in health, is not considered serious.

14.1.6 Unanticipated serious adverse device effect

An untoward medical occurrence that happens in a subject; is related to the investigational device, device procedure, or comparator; is serious; and was

unanticipated is classified as an unanticipated serious adverse device effect (USADE). Serious adverse device effect which are *anticipated* are listed below.

14.2 Reporting period

The reporting period includes any adverse events which occurred between randomization and discharge.

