7.5 Patient Follow-up

Patients will be followed for 30 days +/- 3 days after pSAE. For patients still admitted to the hospital, data will be collected from the medical record. For discharged patients with follow-up at UAB, data will be collected from the medical record. For discharges patients without follow-up, the program manager/research coordinator will contact the patient via telephone to collect relevant data (see section 9 "Data Collection").

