9. DATA COLLECTION

Data is abstracted into an electronic case report form (eCRF) by study staff. The eCRF uses the Research Electronic Data Capture (REDCap) system, a secure research database developed by the NIH. A full list of variables to be collected is shown below. Data logic checks are used to minimize data entry errors.

The following admission parameters will be collected:

- a) Source of patient (transferred from another facility or from the scene of injury?)
- b) Mechanism of injury
- c) Date and time of arrival
- d) Vital signs (temperature, heart rate, blood pressure, respiratory rate)
- e) Use of vasopressors at time of arrival
- f) Intubated at time of arrival
- g) Glasgow Coma Scale (GCS)
- h) Injury Severity Scale (ISS)
- i) Undergoing massive transfusion protocol?

The following blood tests, which are all measured routinely as part of the clinical assessment of trauma patients, are collected, as soon as possible upon arrival:

- a) Arterial blood gas
- b) Hemoglobin and hematocrit
- c) Platelet count
- d) Coagulation parameters including prothrombin time (PT), international normalized ratio (INR), activated partial thromboplastin time (APTT), and Anti-Xa
- e) Thromboelastograph (TEG) or thromboelastogram (ROTEM)

The following data points will be extracted from the initial CT report (emergent):

- a) Phase of enhancement
- b) Splenic injury grade according to AAST guidelines

- c) Signs of accompanying vascular injury such as pseudoaneurysm, extravasation, arterio-venous fistula, or hemoperitoneum
- d) Presence or absence of other intra-abdominal or extra-abdominal trauma

The following data points will be collected from the embolization procedure:

- a) Duration
- b) Radiation dose
- c) Contrast type and volume
- d) Splenic artery diameter
- e) Presence of pseudoaneurysm, arterio-venous fistula, or contrast extravasation on angiography
- f) Embolization material
 - a. Primary (coils vs. vascular plugs)
 - b. Secondary (beads, coils, vascular plugs, foam, other)
- g) Technical success
- h) Intra-procedural complications (non-target embolization, migration of the coil or vascular plug, ineffective treatment requiring splenectomy, vessel rupture, injury at the access site, and splenic infarction/abscess)

The following data points will be collected from the over-read of the CT (non-emergent):

- a) Phase of enhancement
- b) Splenic injury grade according to AAST guidelines

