- c) Signs of accompanying vascular injury such as pseudoaneurysm, extravasation, arterio-venous fistula, or hemoperitoneum
- d) Presence or absence of other intra-abdominal or extra-abdominal trauma

The following data points will be collected while the patient is admitted after the embolization procedure:

- a) Amount of blood products required

- b) Length of stay (ICU, floor, and total)
- c) Delayed complications (Abscess, bleeding, infarction, acute kidney injury)
- d) Secondary splenectomy (i.e. splenectomy needed after embolization)

The following data points will be collected at the 30 day follow up:

- a) Delayed complications (Abscess, bleeding, infarction, acute kidney injury)
- b) Secondary splenectomy

...

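### The adverse-event reporting period in section 14.2 ends at discharge, while complications are collected to day 30, so events that begin after discharge have no stated reporting period

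*Combined protocol and SAP*

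**What the plan says.** Section 14.2 is one sentence: "The reporting period includes any adverse events which occurred between randomization and discharge". No other section states a start or an end for safety reporting.

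Follow-up runs longer. Section 7.5 says "Patients will be followed for 30 days +/- 3 days after pSAE", using the medical record, or a telephone call for discharged patients with no visit at the hospital. In section 9, the list introduced by "The following data points will be collected at the 30 day follow up" covers delayed complications (abscess, bleeding, infarction and acute kidney injury) and secondary splenectomy. The same items are also collected during the admission.

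Section 14.3.2 names splenectomy for ineffective treatment (~10%) and splenic infarction or abscess (~3%) as anticipated device effects. It names contrast nephrotoxicity or allergy (~1%) as an anticipated serious adverse event. Serious cases need a form sent to the Trial Office within 48 hours, and anticipated ones are forwarded to the medical monitor. Under section 14.3.3, unanticipated ones go to the monitors and the IRB within 3 business days of notification, and to the FDA within 7 days.

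The plan defines an adverse event in two ways. Section 14.1 says "Note that adverse events are non-device-related medical occurrences, whereas adverse effects are caused by the investigational device or procedure", and section 14.1.2 says "If the untoward medical occurrence did involve a trial participant, but was not related to the device, it is an adverse event". Section 14.1.4 says "Adverse device effects are a subset of adverse events".

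**The concern.** Section 9 collects delayed complications and secondary splenectomy a second time at day 30, so the plan expects that some may appear after the patient has gone home. Safety reporting has no matching period. A coordinator who learns on the day-30 call of a readmission for abscess or bleeding has an eCRF field for it. The only stated reporting period, however, closed at discharge.

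The plan's own test of seriousness sharpens this. Sections 14.1.3 and 14.1.5 count an event as serious if it needs a hospital admission or prolongs one. Until discharge the patient is already in hospital, so normally only prolongation can apply. Readmission meets the test but falls after the window.

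At stake is whether a serious late event reaches the Trial Office, the medical monitor and, if unanticipated, the IRB and FDA. As written, that depends on how the person who learns of it reads section 14.

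**Working it through.** There is no planned figure to reproduce. The check sets the sections side by side.

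**1. Who is affected.** Patients discharged before the 30 +/- 3 day contact. For a patient still in hospital then, the 14.2 period runs past the contact and there is no gap.

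**2. Which events are affected.** Section 14.2 depends on when an event occurred. An event that began in hospital and was found at the day-30 chart review is inside the period. Only onset after discharge is outside.

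**3. What 14.2 covers under each definition.**

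- *Adverse events are not device-related* (14.1, 14.1.2, 14.1.3 and the classification step in 14.3). Section 14.1.2 divides adverse events into serious and non-serious, so both kinds stop at discharge. Device effects are not mentioned in 14.2 and have no stated period.
- *Device effects are a subset of adverse events* (one sentence in 14.1.4). Device effects also stop at discharge. Later serious ones then fall outside the 48-hour form and the monitor (14.3.2), and unanticipated ones fall outside the IRB and FDA notices (14.3.3).

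The first definition is the dominant one. Neither gives explicit reporting of device effects that begin after discharge.

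**4. Other definitions that do not fit.** Section 14.1.1 makes every untoward occurrence related to the device, its procedure or the comparator, which leaves little or no room for the unrelated events of 14.1.2. Section 14.3.2 labels contrast nephrotoxicity an adverse event. Section 14.1 would class an occurrence caused by the procedure as an effect, and 14.1.3 excludes occurrences related to trial procedures.

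**5. Scale.** Inputs: 50 patients (section 13.1) and the rates in 14.3.2. Expected number = 50 x rate:

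- splenectomy for ineffective treatment: 50 x 0.10 = 5
- infarction or abscess: 50 x 0.03 = 1.5
- contrast nephrotoxicity or allergy: 50 x 0.01 = 0.5

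The documents give neither the time span of these rates nor the share with onset after discharge. If the rates cover the whole 30 days, the expected post-discharge numbers are 5s, 1.5s and 0.5s for a share s between 0 and 1. That is 0 to 5, 0 to 1.5 and 0 to 0.5. The text points both ways on s. Section 9 lists "ineffective treatment requiring splenectomy, vessel rupture, injury at the access site, and splenic infarction/abscess" among intra-procedural complications, which suggests early events, yet it also lists infarction and abscess as delayed complications. The range is too wide to support a probability.

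**The case against.** The best defence is that general duties already cover late events. Section 12 says "The primary investigators also take responsibility for monitoring the study for safety and unanticipated adverse events/effects". Section 14.3 has the site PI classify any untoward occurrence that is identified. Section 14.4 has the monitor review all events and effects and take problems to the IRB. None of these has a time limit. Section 14.2 could also be read as saying what the period includes without closing it. On the dominant definition, the steps for device effects in 14.3.2 and 14.3.3 carry no time limit, and every late complication is in the eCRF in any case.

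Much of this stands. It shows that the investigators are not relieved of responsibility, and that a careful team might report everything. It does not remove the gap: none of these provisions names day-30 findings or extends the period, and an eCRF entry does not by itself start classification or the 48-hour form. On the 14.1.4 definition, the general duties pull against 14.2.

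Three stronger readings that a reader might infer are not supported:

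- *Anything first found at day 30 is excluded.* The test is when the event occurred, not when it was detected.
- *Late device effects are plainly barred from reporting.* That follows only from the single sentence in 14.1.4.
- *Late kidney injury from contrast falls outside on any definition.* That relies on its label in 14.3.2 alone, which conflicts with 14.1 and 14.1.3.

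**Conclusion.** The mismatch is real and should be fixed. Adverse events with onset between discharge and the day-30 contact lie outside the stated period. Device effects in that interval either have no stated period or lie outside it, depending on the definition used.

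Its size in events is unknown. The conclusion rests on the text and on the assumption that some patients go home before day 30, which section 7.5 provides for; it does not rest on an event rate.

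A reader might infer that the trial's results are compromised. They are not: delayed complications and secondary splenectomy are collected to day 30 in both arms. The section 8 comparisons, the sample size and the feasibility targets do not depend on 14.2. The weakness is confined to safety oversight of discharged patients.

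**What to change.** 1. Reword 14.2 to cover all adverse events and all adverse device effects that occur from randomization through the planned day-30 (+3) follow-up, or discharge if later.
2. Add that any event identified at the day-30 chart review or telephone call goes to the PI for classification and reporting under 14.3.
3. Use one definition of adverse event and one of adverse device effect throughout 14.1 to 14.1.4, 14.3 and 14.3.2. Include 14.1.1 and the label on contrast nephrotoxicity; otherwise the conflict survives the new window.
4. Separately, reconcile the 30-day follow-up in 7.5 with the end of 14.4, which continues enrolment until 25 patients per arm have three months or more of follow-up.

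The first two changes take a sentence or two and use a contact already planned; the third is an edit to the definitions. The downside is a few more event forms and a slightly higher reported event count.

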14.3 Reporting procedure

All members of the patient management teams will be instructed as to the possible adverse events prior to the start of the trial and will be given an emergency contact number to immediately report any suspected adverse event to the site investigators.

Any possible untoward medical occurrence is identified will be evaluated and classified by the site PI, as follows:

- a) Relation to the devices: "Effect" (device-related) vs "event" (device-unrelated)
- b) Seriousness: Serious (meeting the criteria listed above) or not
- c) Anticipated: Anticipated (matching the conditions shown in the list below) or unanticipated

14.3.1 Adverse events (AE)/adverse device effects (ADE)

Adverse events and adverse device effects which are not deemed serious will be recorded using the "PHOXSTAT Adverse Event Recording Form".

14.3.2 Anticipated serious adverse events/serious adverse device effects (SADE)

Anticipated adverse device effects include:

- a) non-target embolization (<1%)
- b) migration of the coil or vascular plug (<1%)
- c) ineffective treatment requiring splenectomy (~10%)
- d) injury at the vascular access site (~1%)
- e) splenic infarction/splenic abscess (~3%)
- f) vessel rupture

Anticipated serious adverse events include:

- a) Given that iodinated contrast is used during the procedure, there is a very low risk for nephrotoxicity or allergic reaction to contrast (~1%).

Anticipated serious adverse events and adverse device effects will also be recorded using the "ELSA Adverse Event Recording Form". In addition, a "ELSA Serious Adverse Event/Serious Adverse Device Effect" form must be completed, and emailed to the ELSA Trial Office within 48 hours. All reports of anticipated serious adverse events/SADE will be forwarded to the medical monitor.

14.3.3 Unanticipated serious adverse events/serious adverse device effects (USADE)

Unanticipated serious adverse events and adverse device effects will also be recorded using the "ELSA Adverse Event Recording Form". In addition, a "ELSA Unanticipated Serious Adverse Event/Serious Adverse Device Effect" form must be completed, and emailed to the ELSA Trial Office within 48 hours. In addition, the Study PI must be notified, by telephone within 48 hours.

On notification of a USAE/USADE report, the ELSA Trial Office will, within 3 business days:

- a) Forward the report to the medical monitors
- b) Notify the UAB IRB

In addition, the ELSA Trial Office will, within 7 days, notify the FDA, using the MedWatch form.

14.4 Role and responsibility of the Independent Medical Monitor

Independent medical monitors will review all adverse events/effects and provide an unbiased written report of the events. At a minimum, the medical monitors must comment on the outcomes of the event or problem and in case of an serious adverse event/serious adverse device effect, comment on the relationship to participation in the trial.

If the death is considered unexpected and is either suspected or probably due to treatment, this event will be promptly reported to the medical monitor, who must indicate

whether he/she concurs with the details of the report provided by the principal investigator.

[name] (Division Chief, Acute Care Surgery) is the independent medical monitor for this study. He has committed to comply with the following statements:

The monitor:

- a) Is independent of the research team.
- b) Possesses sufficient educational and professional experience to serve as a subject advocate.
- c) Will promptly report discrepancies or problems to the IRB.

All follow up data to be collected while the patient is at UAB Hospital would already be collected, regardless of study participation. Again, data collected during the course of the research will be kept strictly confidential and accessed only by members of the trial team. Participant's details are stored within REDCap, a secure database used throughout the institution. Regular checks and monitoring are in place to ensure compliance. The data manager (in collaboration with the principal investigators) manages access rights to the data set. Participants are allocated an individual specific trial number and their details are anonymized. Regarding patient follow-up, the study doesn't require that the patient participate in any additional follow up than they would otherwise do if not enrolled in the study. The research coordinator will supplement follow up by making inquiries into the patient's subsequent condition at 30 days through the patient's chart. If no follow up is documented in the chart, then the research coordinator will attempt to conduct a telephone interview with the patient. However, we recognize that patients may drop-out of the study due to lack of follow-up. We will plan to continue enrolling patients until we have at least three months of post-procedure follow-up on the requisite 25 patients in each arm.

